19.0 Budget

- 19.1 Costs charged to patient: routine clinical care and Prevnar 13® vaccine.
- 19.2 Tests to be research funded: Research bloods and associated correlative studies (see Section 14), and lenalidomide will be research funded.

Appendix I
NYHA Classification

Class I: NO Symptoms with ordinary activity

Class II: Symptoms with ordinary activity

Class III: Symptoms with minimal activity

Class IV: Symptoms at rest

Appendix II
Rai Classification

- 0 lymphocytosis ($> 5 \times 10^9/L$)
- I lymphocytosis and lymphadenopathy
- II lymphocytosis and splenomegaly +/- lymphadenopathy
- III anemia (Hgb < 11 g/dL)
- IV thrombocytopenia (platelets $< 100 \times 10^9/L$)

Appendix III ECOG Performance Status Scale	
Grade	Descriptions
0	Normal activity. Fully active, able to carry on all pre-disease performance without restriction.
1	Symptoms, but ambulatory. Restricted in physically strenuous activity, but ambulatory and able to carry out work of a light or sedentary nature (e.g., light housework, office work).
2	In bed <50% of the time. Ambulatory and capable of all self-care, but unable to carry out any work activities. Up and about more than 50% of waking hours.
3	In bed >50% of the time. Capable of only limited self-care, confined to bed or chair more than 50% of waking hours.
4	100% bedridden. Completely disabled. Cannot carry on any self-care. Totally confined to bed or chair.
5	Dead.

Appendix IV
Grading Scale for Hematologic Toxicity in CLL Studies¹

Decrease from Pretreatment value (%)	Grade ²	
	Platelets ^{3, 5}	Hemoglobin ^{4, 5}
No change - 10%	0	0
11-24%	1	1
25-49%	2	2
50-74%	3	3
≥ 75%	4	4

1. A decrease in circulating granulocytes is not being considered since it is not a reliable index in CLL.
2. Grades: 1–mild; 2–moderate; 3–severe; 4–life–threatening. Grade 5 (fatal) toxicity can potentially occur at any level of decrease from pretreatment values and will be recorded as such.
3. If, at any level of decrease the platelet count is $<20,000/\mu\text{L}$, this will be considered grade 4, unless the initial platelet count was $\leq 20,000 \mu\text{L}$ in which case the patient is inevaluable for toxicity referable to platelet counts.
4. Baseline and subsequent hemoglobin determinations must be immediately prior to any given transfusions.
5. If, at any level of decrease from the baseline value the platelet and/or hemoglobin counts are within normal limits, this will be considered a grade 0.

* Hallek BD, et al.: Guidelines for the diagnosis and treatment of chronic lymphocytic leukemia: a report from the International Workshop on Chronic Lymphocytic Leukemia updating the National Cancer-Institute- Working Group 1996 guidelines: Blood 111:54465456, 2008.

Appendix V
PATIENT MEDICATION DIARY

Patient Instructions

- Take at the same time each day with or without food.
- Please indicate on the calendar below *every* day that you take your study medication by placing the dose taken on the line under the date.
- If you miss a dose, place a check “0” under the date, but remember to take your prescribed dose at the next regularly scheduled time.
- Bring *all* bottles and any unused study medication along with this diary when you return for your next appointment.
- Lenalidomide capsules should be swallowed whole, and should not be broken, chewed or opened.

Medication(s)	Dose
Lenalidomide	Days 1-14: 2.5 mg Days 15-42: 5 mg (unless dose is reduced due to adverse events)

Study Drug	Day 1	Day 2	Day 3	Day 4	Day 5	Day 6	Day 7
Date							
Lenalidomide							

Study Drug	Day 8	Day 9	Day 10	Day 11	Day 12	Day 13	Day 14
Date							
Lenalidomide							

Study Drug	Day 15	Day 16	Day 17	Day 18	Day 19	Day 20	Day 21
Date							
Lenalidomide							

Study Drug	Day 22	Day 23	Day 24	Day 25	Day 26	Day 27	Day 28
Date							
Lenalidomide							

Study Drug	Day 29	Day 30	Day 31	Day 32	Day 33	Day 34	Day 35
Date							
Lenalidomide							

Study Drug	Day 36	Day 37	Day 38	Day 39	Day 40	Day 41	Day 42
Date							
Lenalidomide							

Date: _____ Participant’s Signature _____

Appendix VI – Kit Instructions

Impact of Short Term Lenalidomide on Immune Response to Plevnar 13® in Individuals with Chronic Lymphocytic Leukemia (CLL), Small Lymphocytic Leukemia (SLL), and Monoclonal B cell Lymphocytosis (MBL)

Blood Collection Kit Mayo Clinic CLL Laboratory Specimen Checklist and Shipping Instructions

**** PLEASE AVOID DRAWING OR SENDING SPECIMENS ON FRIDAYS AND HOLIDAYS****

Kit Contents:

- 5 lb Styrofoam box and cardboard mailing sleeve
- Patient Information Form
- FedEx Airbill with pre-printed return address
- Five 10ml Sodium Heparin (green top) collection tubes
- Two 10ml Red Top collection tubes
- Absorbent tube holder
- Zip lock specimen bag
- (1) Kool-PAK. Place the ice pack in the freezer for at least 24 hours prior to specimen shipment. Allow the frozen ice pack to thaw at room temperature for 2-3 hours before preparing the specimen for shipment.

Packing and Shipping Instructions:

1. Collect the following specimens:
 - Peripheral blood – Draw:
 - 50ml in five (5) Sodium Heparin tubes (**All Time Points**)
 - 20ml in two (2) Red Top tubes (**Baseline and Day 43 visit**)
2. Label specimens with protocol number MC138E, patient's initials (last name, first name), study patient ID number (if available) and date of collection.
3. Place the slightly thawed Kool-PAK in bottom of Styrofoam container.
4. Place absorbent toweling on top of Kool-PAK.
5. Place the tubes in the absorbent holder and seal in the zip lock specimen bag.
6. Wrap the filled specimen bag in paper toweling and place in the Styrofoam container. Do not place the specimens directly on the ice pack.
7. Place the Styrofoam container and the completed Patient Information Form within the cardboard mailing sleeve.
8. Prepare the package for shipping, applying packing tape as needed. Complete the sender portion of the return FedEx Airbill. Ship specimens priority overnight delivery the same day as collected.
9. Notify Federal Express for pick-up and/or leave package at the designated FedEx drop-off location. **Please e-mail [REDACTED] or call [REDACTED] to notify the laboratory when specimens are being shipped.** The samples in prepared kits should be shipped to the following:

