4.0 Test Schedule

Tests & Procedures	Active Monitoring Phase				
	Days Prior to Registration	Day 15 (+/- 3 days)	Day 28 (+/- 7 days)	Day 43 (+/- 4 days)	Observation: 28 days after end of first cycle (Day 72 +/- 10 days)
	≤14 days				
Medical history	X				
Adverse event assessment	X	X		X	X
Physical exam, including PS, weight and vital signs	X			X	X
Height	X				
Register in the REVLIMID REMS® program (Arm A only)	X ⁸				
Counseling for the REVLIMID REMS® program (Arm A only)			X		
Tumor measurement by physical exam	X ¹			X ¹	
Peripheral blood immunophenotyping by flow cytometry	X ²				
CBC with differential and reticulocytes	X	X		X	X
Serum pregnancy test	X ³	X ³	X ³	X ³	
Chemistry group (SGOT [AST], SGPT [ALT], total bilirubin, serum creatinine, calcium, alkaline phosphatase, uric acid, LDH, potassium)	X	X		X	
Glucose	X				
Direct bilirubin	X ⁷				
CD38	X ²				
ZAP-70	X ²				
IGHV	X ⁴				
CD49d	X ⁴				
Serum protein electrophoresis	X			X	
Beta-2-microglobulin	X				
Peripheral blood CLL FISH panel	X ⁶				
Serum quantitative immunoglobulins (IgG, IgA, IgM)	X			X	
Coombs test (monospecific direct coombs IgG and C3)	X				
EKG	X				
Quantitative T & B cells, peripheral blood	X			X	

Prevna 13 pneumococcal vaccination		X			
Research blood specimens (see Section 14.0)	X ^{5,R}	X ^{5,R}		X ^{5,R}	

1. Physical exam should measure the spleen and liver noting the maximal distance below the respective costal margins and should record the bidimensional diameter of the largest palpable node in each area of involvement including the following sites: left neck (sub-mandibular, cervical, supra-clavicular), right neck (sub-mandibular, cervical, supra-clavicular), left axillary, right axillary, left groin (inguinal, femoral) and right groin (inguinal, femoral).
 2. May be waived for patients who have previously had full flow immunophenotyping consistent with CLL performed at Mayo Clinic. Similarly, if the patient has previously had CD38 and/or ZAP-70 testing performed at Mayo Clinic, repeat assay is elective after discussing with the study chair.
 3. For women of childbearing potential only. Must follow pregnancy testing requirements as outlined in the Revlimid REMS® program material.
 4. If patient has previously had done clinically at Mayo Clinic, this does not need to be repeated.
 5. Blood specimens will be collected and submitted at baseline, Day 15 and Day 43. Kits are required.

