6.12 Correlative Research

A mandatory correlative research component is part of this study, the patient will be automatically registered onto this component (see Sections 3.19e and 14.0).

- 6.13 Documentation of IRB approval must be on file in the Registration Office before an investigator may register any patients.

In addition to submitting initial IRB approval documents, ongoing IRB approval documentation must be on file (no less than annually) at the Registration Office (fax: [REDACTED]). If the necessary documentation is not submitted in advance of attempting patient registration, the registration will not be accepted and the patient may not be enrolled in the protocol until the situation is resolved.

When the study has been permanently closed to patient enrollment, submission of annual IRB approvals to the Registration Office is no longer necessary.

- 6.14 Prior to accepting the registration, the registration/randomization application will verify the following:
- IRB approval at the registering institution
 - Patient eligibility
 - Existence of a signed consent form
 - Existence of a signed authorization for use and disclosure of protected health information
- 6.15 At the time of registration, the following will be recorded:
- Patient has/has not given permission to store and use his/her sample(s) for future research of CLL at Mayo.
 - Patient has/has not given permission to store and use his/her sample(s) for future research to learn, prevent, or treat other health problems.
 - Patient has/has not given permission for MCCC to give his/her sample(s) to researchers at other institutions.
- 6.16 Treatment on this protocol must commence at Mayo Clinic Rochester, Mayo Clinic Arizona, or Mayo Clinic Florida institution under the supervision of a medical oncologist or hematologist.
- 6.17 Treatment cannot begin prior to registration and must begin ≤ 21 days after registration.
- 6.18 Pretreatment tests/procedures (see Section 4.0) must be completed within the guidelines specified on the test schedule.
- 6.19a All required baseline symptoms (see Section 10.6) must be documented and graded.
- 6.19b Study drug (Pevnar 13®) is available on site.
- 6.2 Randomization Procedures
- 6.21 The factors defined in Section 5.0, together with the registering membership, will be used as stratification factors.

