14.0 Body Fluid Biospecimens

- 14.1 The collection of blood/blood products is **mandatory** for the translational/pharmacologic research component of this study.
Summary Table of Research Blood and Body Fluid Specimens to be Collected for this Protocol

Correlative Study (Section for more information)	Mandatory or Optional	Blood or Body Fluid being Collected	Type of Collection Tube (color of tube top)	Volume to collect per tube (# of tubes to be collected)	Baseline	Day 15 visit	Day 43 visit	Process at site? (Yes or No)	Temperature Conditions for Storage /Shipping
T cell immune function (repertoire, synapse) and plasma cytokine profile (14.21)	Mandatory	Whole Blood	Sodium heparin (green)	10 mL (5)	X	X	X	No	Refrigerate/ Cold pack.
Specific immune response to Pevnar 13 vaccination (Streptococcus pneumoniae IgG antibodies,, OPA)(14.22)	Mandatory	Serum	(red top)	10 mL (2)	X	X	X	No	Refrigerate/ Cold pack.

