14.3 Blood Products Handling

14.31 **Kits are required for this study for non-Mayo Rochester sites.**

The kit contains supplies and instructions for collecting, processing, and shipping specimens.

Participating institutions may obtain kits by e-mailing [REDACTED]. E-mail requests should include the site address, contact information and number of kits being requested.

Kits will be sent via FedEx® Ground at no additional cost to the participating institutions. **Allow 3 to 4 business days to receive the kits.**

14.32 Label specimen tubes with protocol number, patient initials (last name, first name), study patient ID number (if available) and date of collection.

14.33 Collect all peripheral blood according to specific kit instructions (see Appendix VI) and table above.

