16.3 Analysis Plan: The analysis for this trial will commence at planned time points (see 16.2) and at the time the patients have become evaluable for the primary endpoint. Such a decision will be made by the Statistician and Study Chair, in accord with CCS Standard Operating Procedures, availability of data for secondary endpoints (eg, laboratory correlates), and the level of data maturity. It is anticipated that the earliest date in which

the results will be made available via manuscript, abstract, or presentation format is when last patient has been followed for at least 2 months.

16.31 Primary Endpoint:

16.311 Definition: The primary endpoint of this trial is the rate of response to the Prevnar 13 vaccine, which will be compared between the two arms. A response will be defined as a four-fold rise from pre-vaccine (day 15) to 28 days after immunization (day 43) for ≥ 2 of the 3 serotypes studied by opsonophagocytic activity (OPA) of antibodies from sera. Patients who are not evaluated for the OPA titers at both pre-vaccine (day 15) and day 43 due to a missed blood draw or other reasons will be considered a non-responder. All patients meeting the eligibility criteria who have signed a consent form and received the Prevnar 13 vaccine will be evaluable for response, with the exception of patients who are determined to be a major treatment violation or flagr.

16.312 Estimation: The proportion of successes will be estimated in each arm by the number of successes divided by the total number of evaluable patients. Ninety-five percent confidence intervals for the true success proportion will be calculated in each arm based on the normal approximation. Comparison of response rates between the two treatment groups will be performed using a one-sided z-test (based on normal approximation with pooled variance of standardized test statistics) at significance level 0.16.

16.32 Secondary Endpoints:

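### The kit sheet omits Day 15 from the serum draw, although Day 15 serum is the pre-vaccine reference for the primary endpoint

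*Combined protocol and SAP*

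**What the plan says.** The instructions for the serum (red-top) tubes disagree.

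- **Appendix VI, Packing and Shipping Instructions, step 1:** "20ml in two (2) Red Top tubes (Baseline and Day 43 visit". The line above it asks for the heparin tubes at every time point, so the restriction on the red-top tubes reads as intended.
- **Section 14.1 table:** the row headed "Specific immune response to Pevnar 13 vaccination" covers the OPA and IgG assays. It is marked mandatory, specifies two red-top tubes, and is ticked at Baseline, Day 15 and Day 43.
- **Section 4.0, footnote 5:** "Blood specimens will be collected and submitted at baseline, Day 15 and Day 43".
- **Section 14.33:** "Collect all peripheral blood according to specific kit instructions (see Appendix VI) and table above". Neither source is given precedence.

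On who uses the sheet, Section 14.31 says "Kits are required for this study for non-Mayo Rochester sites", and Section 6.16 says "Treatment on this protocol must commence at Mayo Clinic Rochester, Mayo Clinic Arizona, or Mayo Clinic Florida institution".

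On the endpoint, Sections 2.11, 11.1, 16.11 and 16.311 all measure the four-fold rise in OPA titer from the Day 15 pre-vaccine sample. Section 16.311 provides that a patient without OPA titers at both Day 15 and Day 43 "due to a missed blood draw or other reasons will be considered a non-responder".

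**The concern.** The specimen left off the sheet is the denominator of every patient's fold rise. Baseline cannot be read as another name for Day 15, because the Section 14.1 table gives them separate columns and footnote 5 lists them separately. The vaccine is scheduled for Day 15 (Section 7.1), so once it is given no pre-vaccine serum can be obtained.

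The plan has no other route to the primary endpoint for such a patient. No section lets the registration serum stand in for the Day 15 serum, and in Arm A that sample precedes 14 days of lenalidomide. Nor does the plan replace the patient. A vaccinated patient stays evaluable under Section 16.311. Section 13.7 replaces only Arm A patients who took lenalidomide but were not vaccinated. The six extra patients in Section 16.22 cover ineligibility, cancellation, major violation and failure to receive vaccine, not a missed draw.

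Each loss therefore stays in the analysis as a failure, whatever the vaccine did. If losses fall about equally on the two arms, both observed response rates shrink towards zero, the difference between them narrows and power falls. The correlative OPA and IgG fold changes (Sections 2.31 and 2.32) lose the same reference sample.

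**Working it through.** **1. The instructions side by side (red-top serum tubes)**

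| Source | Baseline | Day 15 | Day 43 |
|---|---|---|---|
| Section 14.1 table | yes | yes | yes |
| Section 4.0, footnote 5 (all research blood) | yes | yes | yes |
| Appendix VI, step 1 | yes | not listed | yes |
| Needed for the primary endpoint (16.311) | no | yes | yes |

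The table contains everything on the sheet and more. A site that follows both loses nothing; a site that follows the sheet alone loses the Day 15 sample.

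**2. Reproducing the planned power**

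Inputs from Sections 16.21 and 16.312: n = 26 per arm, response rates p1 = 0.10 and p2 = 0.30, one-sided level 0.16, z-test with pooled variance. The critical value is z = 0.9945 at exactly 0.16 (Section 16.211 uses 0.988).

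Power = Φ[(p2 − p1 − z·s0)/s1], where s0 = √(2·p̄(1 − p̄)/n), s1 = √([p1(1 − p1) + p2(1 − p2)]/n) and p̄ = (p1 + p2)/2.

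- p̄ = 0.20; s0 = √(2 × 0.20 × 0.80/26) = 0.1109
- s1 = √((0.09 + 0.21)/26) = 0.1074
- Power = Φ[(0.20 − 0.9945 × 0.1109)/0.1074] = Φ(0.835) = 79.8%, which agrees with the stated 80%.

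**3. Effect of missing Day 15 serum**

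Let f be the share of evaluable patients in each arm without Day 15 serum, assumed equal in both arms and unrelated to true response. Scoring them as non-responders multiplies both rates by (1 − f). For f = 1/6, the rates are 0.0833 and 0.25, p̄ = 0.1667, s0 = 0.1034, s1 = 0.1007, and power = Φ[(0.1667 − 0.9945 × 0.1034)/0.1007] = Φ(0.634) = 73.7%.

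| f | Observed rates | Power, normal approximation | P(z > 0.988), exact binomial |
|---|---|---|---|
| 0 | 10.0% / 30.0% | 79.8% | 82.1% |
| 1/26 | 9.6% / 28.8% | 78.5% | 81.0% |
| 2/26 | 9.2% / 27.7% | 77.1% | 79.8% |
| 1/12 | 9.2% / 27.5% | 76.9% | 79.6% |
| 0.10 | 9.0% / 27.0% | 76.3% | 79.1% |
| 3/26 | 8.8% / 26.5% | 75.7% | 78.5% |
| 1/6 | 8.3% / 25.0% | 73.7% | 76.7% |
| 1/3 | 6.7% / 20.0% | 66.6% | 70.3% |
| 0.50 | 5.0% / 15.0% | 58.3% | 64.1% |

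The exact column is not power at level 0.16. With both true rates at 10%, the rule z > 0.988 rejects with probability 19.2%. That column is useful only for the size of the fall, which is similar.

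**4. What f might be**

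f = s × q, where s is the share of patients at sites using the kit sheet and q is the share of those for whom the sheet alone is followed. The documents give neither. If s = 1/3, then q = 0.25, 0.5 and 1 give f = 1/12, 1/6 and 1/3. If only sites other than Rochester use the sheet, f = 0.50 requires at least half of all patients to be enrolled there and, at exactly half, every one of them to miss the draw; it is an extreme bound.

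**The case against.** The best reply is that the protocol already requires the sample. Section 14.33 names the kit instructions and the table together, so working from the sheet alone does not comply with it. The table marks the draw mandatory, footnote 5 repeats Day 15, and the kit contents list two red-top tubes with no limit by visit. The quarterly review in Section 16.351 might also reveal the problem before many samples were lost. This is why the loss is conditional. It does not remove the contradiction: Appendix VI is the collection checklist for the kit, and it names the visits at which serum is drawn. Detection is not assured either, because sera are stored and shipped in batches for OPA testing (Section 14.22).

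Three further points stand as limits:

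- The loss rates are assumptions, and the cases of one to three patients per arm cost only 1.3 to 4.1 points of power.
- The number of exposed sites is unsettled. Section 14.31 confines the kit requirement to sites other than Rochester, but footnote 5 states it without a site limit.
- Section 6.21 says that the listed factors, "together with the registering membership, will be used as stratification factors", but it does not define that term, and Sections 5.0 and 16.21 omit it. Reading it as clinical site is an inference. Roughly equal expected loss in the two arms follows from randomization in any case.

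Finally, the trial-level endpoint can still be computed, because Section 16.311 assigns an outcome. What is lost is the individual patient's fold rise. That rule is prespecified and is not in dispute.

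**Conclusion.** The concern holds. Appendix VI contradicts the Section 14.1 table and footnote 5 on the one specimen that the primary endpoint cannot do without. Following the sheet alone turns a vaccinated patient into an automatic non-responder, and the sample cannot be recovered.

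The case for correcting it before sites rely on the sheet rests on that irreversibility, not on a predicted loss. The power figures are illustrations. They assume equal loss in both arms, true rates of 10% and 30%, and loss unrelated to response. On those assumptions power falls from 79.8% to 75.7% with three losses per arm and to 66.6% with a third lost. No bias between arms is alleged.

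**What to change.** **Required.** Change the red-top line in Appendix VI, step 1, so that the two tubes are drawn at Baseline, Day 15 (before vaccination) and Day 43, matching the Section 14.1 table.

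**Useful but not essential.** Add a sentence to Section 14.33 stating that the Section 14.1 table governs if the two differ.

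**Optional, and only if a patient is found to lack Day 15 serum because of the sheet.** Keep the Section 16.311 rule for the primary analysis. Add a sensitivity analysis using the registration serum, labelled as not equivalent because in Arm A it precedes 14 days of lenalidomide.

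**Cost.** One line in the kit sheet and, if wanted, one sentence in Section 14.33. The Day 15 visit and draw are already scheduled and the kit already holds the tubes.
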